11.3.2. Secondary outcomes

Binding antibodies - changes from baseline will be expressed as geometric mean fold ratios (GMFR), calculated as the ratio of the post-booster GMC to the baseline GMC. GMCs will be compared between the two vaccine groups and between the vaccine and control groups at 6, 12, 18, 24 and 30 months. We will account for age in the analysis.

Functional antibodies seven time points for vaccine groups [baseline, 1, 6, 12, 18, 24 and 30 months] and six time points for controls [baseline, 6, 12, 18, 24 and 30 months] – for the C-PASS assay (sVNT), data are reported as percentage (%) inhibition by neutralising antibodies using the manufacturer’s instructions. A <30% inhibition is considered negative, while ≥30% inhibition is considered positive. Data will be presented as mean and standard deviation.

Neutralizing assay (20% subset of samples at all time points) up to 12 months – Data will be reported as endpoint titre calculated using the Reed/Muench method (23). A titre of 10 reflects undetectable neutralizing activity.

Cellular immunity: (on a 50% subset at seven time points for vaccine groups and six time points for controls)

Quantiferon COVID IFNy release assay up to 12 months – Levels of IFNy will be reported in IU/ml according to the manufacturer’s instructions. Data will be reported as GMT and 95% confidence intervals.

IFNy Elispot – The number of IFNy-producing cells/million PBMCs will be reported using means and 95% confidence intervals.

Intracellular cytokine staining – The data will be reported as the frequency (%) of cytokine-expressing T cells (e.g., total T cells, CD4 T cells, CD8 T cells). Cytokines such as IFNy (Th1) and IL-5 (Th2) will be measured as a minimum. This will be presented as means and 95% confidence intervals.

Multiplex cytokine assays – A 10-plex panel of cytokines will be measured in supernatants from the Elispot studies. Cytokine concentrations will be reported in pg/ml, and data will be presented as GMT and 95% confidence intervals.

11.3.3 Exploratory outcome

We will describe the number of confirmed mild, moderate, and severe breakthrough cases in each of the three groups.

Explore the association between immune protection and viral variants and identify potential viral signatures associated with severe breakthrough infections.

12 ETHICS AND DISSEMINATION

12.1 Research Ethics Approval & Local Governance Authorisation

This protocol, the informed consent document, and any subsequent amendments will be reviewed and approved by the human research ethics committee (HREC) before the research. A letter of protocol approval by HREC will be obtained before the commencement of the trial and approval for other trial documents requiring HREC review.

12.2 Amendments to the protocol

This trial will be conducted in compliance with the current version of the protocol. Any change to the protocol document or Informed Consent Form that affects the scientific intent, trial design, participant safety, or may affect a participant's willingness to continue participation in the trial is considered an amendment and, therefore, will be written and filed as an amendment to this protocol and/or informed consent form. All such amendments will be submitted to the HREC for approval before implementation.

12.3 Protocol Deviations and Serious Breaches

All protocol deviations will be recorded in the participant record (source document) and on the CRF and must be reported to the Site Principal Investigator, who will assess for seriousness.

Those deviations deemed to affect to a significant degree the rights of a trial participant or the reliability and robustness of the data generated in the clinical trial will be reported as serious breaches. Reporting will be done promptly (Site Principal Investigator is to report to the Sponsor-Investigator within 72 hours and to the Site RGO within seven days; Sponsor-Investigator is to review and submit to the approving HREC within seven days).

Where non-compliance significantly affects human participant protection or the reliability of results, a root cause analysis will be undertaken, and a corrective and preventative action plan will be prepared. Where protocol deviations or serious breaches identify protocol-related issues, the protocol will be reviewed and, where indicated, amended.

13 CONFIDENTIALITY

Participant confidentiality is strictly held in trust by the participating investigators, research staff, the sponsoring institution, and their agents. This confidentiality is extended to cover the testing of biological samples, genetic tests, and clinical information relating to participating participants.

The trial protocol, documentation, data, and all other information generated will be strictly confidential. No information concerning the trial, or the data will be released to any unauthorised third party without the prior written approval of the sponsoring institution. Authorised representatives of the sponsoring institution may inspect all documents and records required to be maintained by the Investigator, including but not limited to medical records (office, clinic, or hospital) and pharmacy records for the participants in this trial. The clinical trial site will permit access to such records.

All laboratory specimens, evaluation forms, reports, and other records that leave the site will be identified only by the Participant Identification Number (SID) to maintain participant confidentiality.

Clinical information will not be released without the participant's written permission except as necessary for monitoring by HREC or regulatory agencies.

Data will be shared with relevant government bodies.

14 PARTICIPANT REIMBURSEMENT

Study participants will be compensated for their time, the inconvenience of blood tests and procedures, and travel expenses (parking or public transport reimbursement).

15 FINANCIAL DISCLOSURE AND CONFLICTS OF INTEREST

No conflict of interests.

16 DISSEMINATION AND TRANSLATION PLAN

Participants will be given access to their personal antibody levels and the analysed data at each time point once it becomes available. The former will be on request at follow-up visits, while the latter and the overall study results will be provided by group email as the analysed antibody data becomes available.

After study completion, a major publication will be prepared for an international journal. The data will also be presented at appropriate international conferences and meetings.

17 ADDITIONAL CONSIDERATIONS

Not applicable.

19 APPENDICES

APPENDIX 1 – Product information sheets

Moderna bivalent
Pl.pdf

Nuvaxovid_PIL.pdf

ModernaBA4_5_Pl.p
df

9.1	PLANNED TABLES AND FIGURES	35
10	REFERENCES	43

LIST OF ABBREVIATIONS

AE	Adverse Event
AIR	Australian Immunisation Register
BTI	Breakthrough infection
CMI	Cell-mediated immunity
ELISA	Enzyme-Linked Immunosorbent Assay
GM	Geometric Mean
GMC	Geometric Mean Concentration
GMR	Geometric Mean Ratio
ICH	International Council for Harmonisation
PBMC	Peripheral blood mononuclear cells
PCR	Polymerase Chain Reaction
RAT	Rapid Antigen Test
SAE	Serious Adverse Event
SAP	Statistical Analysis Plan
SD	Standard Deviation
SE	Standard Error
SOC	System Organ Class
MCRI	Murdoch Children's Research Institute
RBD	Receptor Binding Domain
RCH	Royal Children's Hospital
VoC	Variant(s) of concern

1 ADMINISTRATIVE INFORMATION

Protocol: 91108; Version 8.0, 4 Dec 2024

ClinicalTrials.gov Identifier: NCT05658523

1.1 DOCUMENT VERSION HISTORY

Version Date	Version	Author	Change Description	Reason/Comment
19/3/2024	1.0	[name]	Initial release.	Not applicable.
20/3/2025	2.0	[name]	Adding analysis plans for outcomes up to 30 months	Follow-up has been extended

1.2 SCOPE OF THIS DOCUMENT

This statistical analysis plan (SAP) outlines analyses of data up to Month 30. A previous SAP (dated 19/3/2024) focused on analyses of data up to and including Day 28 visit.

1.3 SUMMARY OF CHANGES COMPARED TO THE PROTOCOL

- The primary objective as worded in the protocol is to *“Assess and compare the immune response in two randomised vaccine groups (bivalent Moderna and Novavax) at 28 days post-vaccination measured as binding antibodies (IgG ELISA – Wuhan and/or Omicron) who have been boosted at least six months earlier.”* In this SAP, binding antibodies for Wuhan will be treated as the primary outcome, with other (sub)variants (e.g. Omicron BA.1 and Omicron BA.4/5) treated as secondary outcomes.
- The protocol specified that binding IgG data using the Euroimmun S1 IgG ELISA kits will be reported as relative units/ml (RU/ml) per the manufacturer’s instructions, with the units converted to BAU/ml for Wuhan. Whereas they will remain RU/ml for Omicron BA.1. For the Omicron BA.4/5 binding IgG data, an in-house ELISA will be used, the units are EU/ml.
- The protocol specified two different sets of adjustment variables to be included in the linear regression model for the primary analysis of the primary immunogenicity endpoint (IgG at Day-28). In this SAP, the adjustment variables have been updated to be: age group, baseline levels, first booster vaccine and time since the first booster.

2 STUDY OBJECTIVES

2.1 PRIMARY OBJECTIVES

The primary objectives of the study (as worded in the protocol) are to:

- Assess and compare the immune response in two randomised vaccine groups (bivalent Moderna and Novavax) at 28 days post-vaccination measured as binding antibodies (IgG ELISA – Wuhan and/or Omicron) who have been boosted at least six months earlier.
- Assess the rate and severity of reactogenicity within one-week post-second booster for the Moderna and Novavax groups (Timepoint – daily, for seven days post-vaccination).

2.2 SECONDARY OBJECTIVES

The secondary objectives (as worded in the protocol) are to:

- Assess and compare the immune response in two randomised vaccine groups (bivalent Moderna and Novavax) at 28 days post-vaccination measured as functional antibodies (sVNT and nAB) and cell-mediated immunity (CMI).
- Assess and compare the immune response in two randomised vaccine groups (bivalent Moderna and Novavax) at 6, 12, 18, 24 and 30-months post-vaccination measured as binding antibodies (IgG ELISA), functional antibodies (sVNT and nAb), and CMI.
- To describe binding and functional antibodies in the control group compared with the two vaccine groups (bivalent Moderna and Novavax) at baseline, 6, 12, 18, 24 and 30-months.
- To assess whether a fourth COVID-19 vaccine dose provides an immunological benefit over a third dose by comparing CMI at 6, 12, 18, 24 and 30-months in the control group compared with the two vaccine groups (bivalent Moderna and Novavax).
- To evaluate the safety of fourth booster dose regimens.

Exploratory objectives are:

- To describe the number and severity of breakthrough cases in the control group compared with the two vaccine groups (bivalent Moderna and Novavax) to 30 months post-vaccination.
- To correlate virological markers (viral load and viral genome characteristics) and immunological markers (humoral antibody, CMI) among mild and severe breakthrough cases.

3 STUDY SYNOPSIS AND BACKGROUND

Nb. Full details of the background to the trial and its design are presented in the protocol.

3.1 STUDY DESIGN

This clinical trial is a blinded, two-arm randomised study to determine the safety, reactogenicity and immunogenicity of a fourth dose of SARS-CoV-2 vaccines in Australia in adults 18 years or older who have received their third dose of COVID-19 vaccine, at least six months previously. A separate non-randomised control arm will be enrolled for comparison. The groups are described below. The trial intervention will be a single booster dose of vaccine:

Group	Vaccine given	N
Group A – (Moderna)	Bivalent Moderna (mRNA-1273.214) (Ancestral SARS-CoV-2 25µg + Omicron Variant (B.1.1.529) 25µg). Replaced by Bivalent Moderna (mRNA-1273.222) (Ancestral SARS-CoV-2 25µg + Omicron Variant (BA.4-5) 25µg) when introduced.	225
Group B – (Novavax)	Novavax (5µg of SARS-CoV-2 spike protein adjuvanted with 50µg of Matrix-M)	225
Group C – (Control group)	No vaccine given	150

Note: Unless otherwise stated, all analyses of the Bivalent Moderna vaccine arm (Group A) will comprise data from the Moderna BA.1 and Moderna BA.4-5 groups combined.

3.2 STUDY GROUPS AND RANDOMISATION

The two vaccine groups (Groups A and B) will be randomised 1:1 to one of two interventions (bivalent Omicron-specific Moderna and Novavax) stratified by age (<50 and ≥50 years). An independent statistician from the Melbourne Children's Trial Centre at the Murdoch Children's Research Institute will provide a secure, password-protected web-based randomisation schedule. Blocked randomisation will be used with random blocks of permuted length.

50% of participants from each vaccine group will be included in the cell-mediated immunity (CMI) subgroup analysis. We will ensure that the age strata (<50 and ≥50 years) are equally represented in the CMI vaccine groups.

The control group will not be randomised and will be recruited from participants <60 years of age who indicate that they are not planning to receive a fourth vaccine dose at the time of recruitment. Controls will be recruited into proportional pre-defined age bands (18-29 years, 30-49 years, 50-59 years).

Table 1. Study groups and strata

Group	Age group	Booster vaccine	Dose given	Number
Group A	<50 years	Bivalent Moderna BA.1	50µg	75
	<50 years	Bivalent Moderna BA.4-5	50µg	75
	≥50 years	Bivalent Moderna BA.4-5	50µg	75
Group B	<50 years	Novavax	50µg	150
	≥50 years	Novavax	50µg	75
Group C	<60 years	No vaccine	-	150

3.3 BLINDING

Study staff involved in administering the vaccine will use REDCap to receive the information on the participant's randomisation (study ID) number and vaccine. Study staff will upload vaccination information to the Australian Immunisation Register (AIR) after one week. Participants will remain blinded to their vaccine type until day seven post-vaccination when their vaccination history is uploaded to the AIR. Study staff assessing reactogenicity and immunogenicity will be blinded to each participant's vaccine allocation, which will be hidden in REDCap for blinded study staff. Statisticians and analysts will remain blinded during the development of the SAP and will develop and finalise all codes using a dummy variable for treatment allocation.

3.4 STUDY POPULATION: ELIGIBILITY AND SCREENING

The trial population will be adults 18 years and older who have been boosted at least six months earlier with a third COVID-19 vaccine dose. There will be no upper age limit for groups A (Moderna) and B (Novavax). Only those aged >18 - <60 years will be recruited to group C (controls), as this is the target age group for which the need for additional boosters is not well established. Additional booster doses are strongly recommended for individuals 60 years and over. Procedures will be implemented to ensure an even age distribution for Moderna product transition in each vaccine group.

Inclusion criteria:

Each participant must meet all the following criteria to be enrolled in this trial:

1. Have received a third COVID-19 vaccine dose at least six months before the start of the study.
2. No confirmed SARS-CoV-2 infection by PCR or RAT within the last three months.
3. Willing and able to give written informed consent.
4. Aged 18 years or above.
5. Willing to complete the follow-up requirements of the study.

Subjects with comorbidities other than those listed below as contraindications will be included. Pregnant women or women who may become pregnant will be included.

Exclusion criteria:

Potential participants meeting any of the criteria below will be excluded from this trial:

1. Currently receiving immunosuppressive medication or anti-cancer chemotherapy.
2. Known HIV infection.
3. Congenital immune deficiency syndrome.
4. Received immunoglobulin or other blood products in the three months prior to potential study booster vaccination.
5. Study staff and their relatives.

6. Have a history of a severe allergic reaction to any COVID-19 vaccines or have a medical exemption to receiving further COVID-19 vaccines.
7. Cannot read or understand English.

3.5 SAMPLE SIZE

Sample size calculations were performed using nQuery 8 software and methods described by Van Belle, et al. 1993 (20). Precision-based sample size calculations were performed based on the reactogenicity outcomes. Assuming the percentage of participants reporting local or systemic reactions is 50%, 100 participants will produce a confidence interval that is 9.8 percentage points from the observed percentage. For immunogenicity, sample size calculations were based on comparing day 28 post-booster geometric mean concentrations of IgG antibodies between vaccine arms. We assumed the coefficient of variation (standard deviation/mean) of the post-booster antibody concentrations would be 1.15 (based on data from Munro, et al. 2021 (8), but increased to be conservative). Even though previous studies demonstrated a geometric mean ratio (GMR) of up to 4 between the study vaccine groups, we considered a clinically important difference between groups to be a GMR of >1.4. Based on these assumptions, the study will need to recruit 160 participants in each vaccine group overall to achieve 90% power at a two-sided 0.05 significance level. Allowing for ~20% loss to follow-up, the sample size in each arm was expanded to 200. To ensure age representation (<50 and \geq 50) in the second Moderna bivalent group (BA.4-5) numbers were increased in the younger age group. We are confident that the sample size is sufficient as it is likely that the magnitude of the GMR will be higher than expected and the loss to follow-up lower than anticipated. Note that the original sample size was 200 per group, which changed to 225 in each vaccine group and 150 in the control group.

3.6 STUDY PROCEDURES

Table 2 provides a summary of the study procedures. A participant will be considered lost to follow-up if they fail to return for two consecutive visits and cannot be contacted by the trial staff.

Table 2. Schedule of assessments

Assessments/ activities*	Visit 1	Visit 2	Visit 3	Visit 4	Visit 5	Visit 6	Visit 7
Timing	Day 0	Day 1	Day 7	Day 28	3 months	6 months	12 months
Visit window			+ 3 days	- 3 days + 7 days	+/- 14 days	+/- 14 days	+/- 14 days
Group	A,B,C	A,B	A,B	A,B,C	A,B,C	A,B,C	A,B,C
Location of visits	At RCH	Phone call	Phone call	At RCH (A,B) Phone call (C)	Phone call	At RCH	At RCH
Informed consent	X						
Eligibility confirmation	X						
Randomisation	X (A,B)						
Blood sampling	X			X (A,B)		X	X
Vaccination	X (A,B)						

Vital signs	X (A,B)						
Issue diary card, ruler, and thermometer	X (A,B)						
Collect diary card	X (daily) for vaccine groups (A&B)						
Documentation of Solicited AE	X	X	X				
Documentation of unsolicited AE	X	X	X	X			
Documentation of medically attended AE	X	X	X	X	X		
Documentation of SAE	Throughout study period						
Documentation of confirmed breakthrough SARS-COV-2 infection/ COVID-19	Throughout study period						

*Unless otherwise indicated, assessments/activities are valid for Groups A, B and C.

4 GENERAL STATISTICAL METHODOLOGY

4.1 OBJECTIVES OF THE ANALYSIS PLAN

This analysis plan covers analyses for the primary and secondary objectives, and analyses of breakthrough infections. Analyses of other exploratory objectives will be detailed in a separate plan.

4.2 STATISTICAL SOFTWARE

All analyses will be conducted using Stata Version 18.0.

4.3 VALIDATION OF RESULTS

Data cleaning and verification details, including consistency and range checks, are specified in the Data Management Plan. The analysis of the primary immunological endpoint, including any derivation of outcomes and/or covariates from raw data, will be independently double-programmed by two analysts before unblinding using a randomly generated dummy variable for treatment allocation; discrepancies in results will be resolved by consensus.

4.4 ANALYSIS POPULATIONS

See Estimand-to-Analysis tables for further information on analysis populations.

4.5 MULTIPLICITY ADJUSTMENT

This trial will evaluate multiple outcomes, including multiple (sub)variants for the immunogenicity outcomes (Wuhan, Omicron BA.1, Omicron BA.4/5, Omicron JN.1). To avoid multiple primary outcomes, this SAP has specified binding antibody levels (IgG) for the Wuhan strain at Day-28 as the primary immunological endpoint. For group comparisons, treatment effects with 95% confidence intervals will be presented. Results will be interpreted based on the magnitude of the treatment effects. No multiplicity adjustments have been planned.

Secondary outcome results will be interpreted precisely (including the timepoint and the specific outcome) so that the per-comparison-wise error rate is not increased and adjustment for multiplicity is not required.³

4.6 INTERIM ANALYSES

There will be no interim analyses, however see Section 4.8 for planned Timing of analyses.

4.7 REPORTING

Clinical Study Reports are to be produced for the funder. All analyses will be conducted according to the SAP. However, the formatting of figures and tables may be modified, and additional descriptive (but not comparative) statistics may be provided to comply with the ICH E3 Guidelines on the Structure and Content of Clinical Study Reports.¹

4.8 TIMING OF ANALYSES

Due to the rapidly evolving nature of the pandemic, analyses will be conducted for each immunological endpoint once the necessary data have been cleaned and locked, which will be as soon as is practicable after all participants have completed their Day-28 visit (for Day-28 endpoints), Month-6 visit (for Month-6 endpoints), Month-12 visit (for Month-12 endpoints), Month-18 (for Month-18 endpoints) and Month-24 (for Month-24 endpoint), although some of the longer-term endpoints (e.g. Month-6 and Month-12 results) may be published together. Necessary data for analysis includes those required for the reactogenicity, safety, breakthrough infection endpoints, and data on intercurrent events to the same timepoint as for the

immunological endpoint to be analysed, as these are essential for interpretation. A list of necessary variables is provided in Section 4.9.

4.9 LIST OF NECESSARY VARIABLES

Below is a list of necessary variables that need to be cleaned and locked for the analysis of each immunological endpoint to be triggered, in addition to the immunological parameter itself:

- Trial arm
- Primary series vaccine
- First booster vaccine
- Age group strata
- Dates of first, second and third doses
- Date of trial vaccine for vaccine groups (Day 0)
- Date of blood-draw/study visit
- Reactogenicity for all solicited reactions on 7 days, including grading (Day-28 timepoint only)
- SARS-CoV-2 infection, including clinical spectrum and date of positive test (to relevant timepoint)
- Receipt of additional COVID-19 vaccine doses (yes/no, and date) (to relevant timepoint)
- Adverse events (severity, causality, SOC, seriousness, expectedness, and outcome) (to relevant timepoint)
- Baseline value of the immunological parameter to be analysed

4.10 HANDLING OF MISSING DATA

Exploration of missing data

The number and percentage of participants with missing data will be reported by study arm at each time point. Baseline characteristics of participants with and without missing data will be tabulated. To explore differential drop-out/withdrawal and trajectories of immunological endpoints by withdrawal status, we will plot antibody titres (Wuhan) over time by strata defined by time of withdrawal (separately by trial group).

Multiple imputation will be performed for the primary analysis of immunological endpoints if more than 5% of participants have missing data. Multiple imputation will be performed using multivariate imputation by chained equations (MICE), with logistic regression for binary variables and linear regression for continuous variables (or predictive mean matching if non-normal). Missing values will be imputed separately by trial arm to ensure treatment effects are maintained, and 50 imputations will be produced. The imputation model will include all variables that are included in the primary analysis model, including stratification variables (age group) and baseline levels of the outcome variable. Covariates considered for inclusion in the imputation model as auxiliary variables include primary series vaccine, duration between different doses and study day of blood draw. Where possible, multiple imputation will be performed simultaneously for all immunological outcomes, but it may be necessary to use separate models at different timepoints due to the timing of analyses. The same imputation models will be used for data set to missing for analyses under the hypothetical strategy. See Estimand-to-Analysis tables under specific outcomes for further detail regarding handling of missing data.

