9.4.1 Implementation of the Hypothetical Strategy

Under the hypothetical strategy, outcome values experienced after the specified intercurrent events will be set to missing and multiple imputation will be used to calculate the estimate including these participants. Multiple imputation for analyses under the hypothetical strategy will be carried out using the same imputation procedure used to handle missing data (see Section 4.10). Imputation will be done separately by trial arm. For Month-6, Month-12, Month-18, Month-24 endpoints and Month-30 endpoints, levels of the outcome variable at previous blood draws will also be included in the imputation model.

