9.5 SUBGROUP ANALYSES AND TESTS FOR INTERACTION

Analyses for all endpoints will be conducted amongst all strata combined. Primary analyses will combine data from participants receiving the Moderna BA.1 and Moderna BA.4/5 vaccines. Subgroup analyses stratified by the age strata (<50 and ≥50 years) will also be conducted for the immunological endpoints and breakthrough infection secondary endpoints. Subgroup analyses will also be performed by Moderna vaccine timing (Moderna BA.1 period vs Moderna BA.4/5 period) for immunological endpoints. Tests of interaction will be done by fitting a model with an interaction parameter between study arm and the age strata.

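### The by-arm imputation model names neither Moderna product nor enrolment period, so the planned BA.1-period and BA.4/5-period subgroup GMRs would be pulled together if they are run on imputed data

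*SAP*

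**What the plan says.** **Imputation.** SAP 4.10 specifies: "Missing values will be imputed separately by trial arm to ensure treatment effects are maintained, and 50 imputations will be produced". On content it says: "The imputation model will include all variables that are included in the primary analysis model". In SAP Table 6 those variables are age group, baseline level, first booster vaccine and time since first booster. The auxiliaries that SAP 4.10 says may be considered are primary series, dose intervals and study day of the blood draw. Product and period appear in neither list. SAP 9.4.1 uses the same procedure for the hypothetical strategy ("Imputation will be done separately by trial arm") and adds earlier levels of the outcome from Month 6.

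**The Moderna arm.** Under SAP 3.1, unless otherwise stated, "all analyses of the Bivalent Moderna vaccine arm (Group A) will comprise data from the Moderna BA.1 and Moderna BA.4-5 groups combined". SAP Table 1 plans 75 BA.1 and 75 BA.4-5 recipients under 50, and 75 recipients aged 50 or over, all BA.4-5.

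**The subgroup.** SAP 9.5 states: "Subgroup analyses will also be performed by Moderna vaccine timing (Moderna BA.1 period vs Moderna BA.4/5 period) for immunological endpoints". The only interaction test it specifies is arm by age stratum.

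**When imputation applies.** SAP 4.10 calls for imputation in the primary analysis of the immunological endpoints once more than 5% of participants have missing data. SAP Tables 6, 9 and 10 instead analyse participants with complete data and make imputation supplementary above 5%. Table 14 labels the main analysis complete case. SAP 9.5 does not say which data set the subgroups use.

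**The concern.** Imputing within arm protects the contrast between arms because each arm has its own model. It does not protect a contrast within the Moderna arm that the model cannot see. Below age 50, a missing value for a BA.1 recipient and one for a BA.4-5 recipient are drawn from the same regression, which averages the two products. Any product difference is therefore close to absent among the imputed records.

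The SAP puts one of its two subgroup factors (age group) into the imputation model and leaves out the other (period). The secondary endpoints include BA.1 and BA.4/5 antibodies, the antigens on which the two products differ, so a product difference is plausible. The bias has a fixed direction, towards the two periods looking alike, and running 50 imputations does not reduce it.

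**Working it through.** **1. The plan's own figures.** Inputs from SAP 3.5: "the coefficient of variation (standard deviation/mean) of the post-booster antibody concentrations would be 1.15"; "a clinically important difference between groups to be a GMR of >1.4"; and a size chosen "to achieve 90% power at a two-sided 0.05 significance level".
- Log SD = sqrt(ln(1 + 1.15²)) = 0.918. Log effect = ln 1.4 = 0.336.
- n per group = 2(1.960 + 1.282)² × 0.918² / 0.336² gives 157 (158 with the t distribution), against the stated 160. Power at 160 is 90.6%.
- 160 / (1 − 0.20) = 200, as stated.

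The sample-size figure reproduces. The 20% loss allowance is four times the 5% imputation trigger.

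**2. Expected attenuation.** Let δ be the log ratio of the BA.4/5-period GMR to the BA.1-period GMR, with the product effect in the Moderna arm only. Let m be the share missing at random. Assume that no other imputation variable tracks period. Each period has its own Moderna versus Novavax model, adjusted for age group in the BA.4/5 period. The Novavax cells are assumed to match at 75/75/75, because SAP Table 1 gives Novavax by age only.
- Under 50, the imputation model predicts the midpoint of the two products (75 and 75).
- BA.1 period: the Moderna mean moves up by mδ/2.
- BA.4/5 period, under 50: it moves down by mδ/2. At 50 and over it does not move, because all recipients are BA.4-5 and age group is in the model. Averaged over two cells of 75, the shift is mδ/4.
- What remains is δ(1 − m/2 − m/4) = δ(1 − 0.75m).

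For a true ratio of 1.40: 1.40^0.925 = 1.365 at 10% missing, and 1.40^0.85 = 1.331 at 20%.

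**3. Simulation.** 600 simulated trials with log SD 0.918, an assumed baseline-outcome correlation of 0.5 and values missing completely at random gave 1.36 at 10% and 1.34 at 20%. A second set of 600 runs, with time since first booster in the models but unrelated to period, gave the following.

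| True ratio | Missing | No period term | With period term |
|---|---|---|---|
| 1.40 | 5% | 1.39 | 1.40 |
| 1.40 | 10% | 1.35 | 1.40 |
| 1.40 | 20% | 1.32 | 1.38 |
| 2.00 | 10% | 1.88 | 2.03 |
| 2.00 | 20% | 1.80 | 2.01 |

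Monte Carlo error is about 0.01 to 0.02 on the ratio, so both sets agree with step 2. Complete-case estimates showed no attenuation (1.38 to 1.43 for a true 1.40).

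**4. Variables that partly stand in for period.** In the second set, at 20% missing and a true 1.40:
- If time since first booster differs by 2 SD between periods (assumption), the result is 1.36 instead of 1.32.
- If an earlier sample that carries the product effect is in the model (assumption), the result is also 1.36.

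**5. Size against sampling error.** The SE of the log period contrast without missing data is 0.918 × sqrt(1 − 0.25) × sqrt(2/75 + 2/150) = 0.159. The bias at 20% missing is 0.75 × 0.20 × 0.336 = 0.050, and 0.050 / 0.159 = 0.32 SE. For a true 2.00 it is 0.15 × 0.693 = 0.104, or 0.65 SE.

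**The case against.** **A reader might infer that the planned period comparison is biased as it stands.** The documents do not support that. SAP Tables 6, 9, 10 and 14 make the main analyses complete case, and those are unaffected. The bias arises only if the period subgroup uses imputed data. That condition is not remote, because SAP 4.10 itself assigns imputation to the primary analysis above 5% missing.

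**A reader might extend the point to the hypothetical-strategy analyses**, where much may be set to missing by Month 30. At an assumed 50% missing the formula gives 1.40^0.625 = 1.23. But Table 14 applies that strategy to the overall Moderna versus Novavax estimands and does not cross it with period. The figure therefore joins an assumed missingness level to an analysis the SAP does not specify.

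**A reader might take the attenuation to equal the imputed share**, giving 1.40^0.8 = 1.31 at 20%. That fits one joint model with arm-by-period and arm-by-age terms. SAP 9.5 describes subgroup analyses and specifies no period interaction test. With separate models by period, the correctly imputed values at 50 and over bring the factor down to 0.75.

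**A reader might fear that a false finding of homogeneity would justify pooling the products.** SAP 3.1 and 9.5 already fix the pooling in advance, so this subgroup does not decide it.

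It is also fair to say that the auxiliary list is open, so a period term is not forbidden, and that age group, time since first booster and earlier titres may recover part of the effect. These reduce the attenuation without removing it. What stands is that following the named variables gives a biased subgroup estimate wherever imputed data are used.

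**Conclusion.** The point holds conditionally. The imputation model as named is blind to a factor that SAP 9.5 uses, so period-specific GMRs computed from imputed data are drawn together. For an assumed true ratio of 1.40 the loss is modest, to about 1.36 at 10% missing and 1.34 at 20%, and the 20% bias is under half a standard error. It grows with the missing share and with the true difference.

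These sizes rest on the planned cells, matching Novavax cells, values missing at random, a product effect in the Moderna arm only, and no covariate that tracks period. The pooled Moderna versus Novavax GMR is not the target. This is a worthwhile, nearly free correction and does not threaten the primary result.

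**What to change.** - In SAP 4.10, and so in 9.4.1, add an enrolment-period indicator (Moderna BA.1 period versus BA.4/5 period) to both arms' imputation models. It can be derived from the Day 0 date, which SAP 4.9 already lists among the variables to be locked. It is estimable alongside age group because both products occur under 50.
- In SAP 9.5, state whether the subgroup analyses use complete-case or imputed data.
- Reconcile SAP 4.10 (imputation for the primary analysis above 5% missing) with Tables 6, 9, 10 and 14 (complete-case main analysis).

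The cost is one binary covariate, one degree of freedom, per arm, plus SAP wording. No new data are needed. In the simulations the period term brought the ratio back to 1.38 to 1.40 for a true 1.40.
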